1.2.2. Previous Human Experience with Chimpanzee Adenovirus Vector Serotype 3 (cAd3)

Recombinant chimpanzee adenovirus serotype 3 (cAd3 or ChAd3) is a subgroup C adenovirus with properties similar to those of human adenovirus serotype 5 (Ad5). Both cAd3 and cAd63 vectors were initially considered for development of a new Ebolavirus vaccine based on their immunological properties and because the vectors had already advanced into Phase I human clinical trials. Both the cAd3 and cAd63 were shown to be safe and immunogenic in human studies evaluating candidate vaccines for hepatitis C virus (HCV) [23] and malaria [24], respectively. After initial consideration of these adenoviral vectors, the cAd3 vector was chosen for further development as a candidate vaccine because it appeared more protective against infection in the NHP model.

Serological studies showed a low seroprevalence in human sera for antibodies to cAd3 [25] and unpublished VRC data], and when present, antibody titers are low. Ad5 pre-existing immunity did not appear to cross-react with cAd3 in mice [26, 27] [and unpublished VRC data]. The cAd3-based vaccines were capable of inducing an immune response comparable to human Ad5 vectored vaccines [26, 27]. VRC investigators showed that cAd3 vectors had similar levels of potency as rAd5 using multiple with various antigens including influenza HA and HIV Env [unpublished VRC data].

In a Phase I study, Barnes *et al.* tested two rare serotype adenovirus vectors, cAd3 and human adenovirus serotype 6, each expressing HCV antigens. A total of 41 participants were vaccinated by intramuscular (IM) injection with the dosages up to 7.5×10^{10} viral particles (VP) per injection. Several prime-boost schedules were evaluated with 4-6 participants per treatment group. Overall, these vaccines were assessed as safe and well tolerated. Mostly mild, self-limited local and systemic reactogenicity was observed which was dose-dependent but did not differ significantly between priming and boosting. The vaccinations induced HCV-specific immunity with broad specificity that was sustained for at least 1 year after the boost with heterologous adenoviral vector [23]. Chimpanzee adenoviral vector type 3 vaccines have been safe in healthy adults at dosages up to 2×10^{11} PU per injection in completed and ongoing clinical trials [23, 24].

Published data in support of evaluating cAd3 vectors for a next generation Marburg vaccine comes from the Phase I, dose-escalation, open-label trial of cAd3-EBO performed by Ledgerwood, *et al.* [16]. Twenty healthy adults, sequentially enrolled in two groups of 10, received IM doses of 2×10^{10} particle units or 2×10^{11} particle units. No safety concerns were identified although, transient fever developed within 1 day after vaccination in two participants in the high dose group. Glycoprotein-specific antibodies were induced in all 20 participants, however the high dose group developed antibodies of higher magnitude and more frequent CD4 and CD8 T cell responses to vaccine antigen. Other studies evaluating this product in U.S., Swiss

and Malian adults showed the Ebola cAd3 vaccine to be safe and immunogenic [16-19]. Similar cAd3 Marburg GP doses will be tested in this slowly enrolling, staged, dose-escalation study.

In summary, use of the recombinant, non-replicating cAd3 vector for construction of the cAd3-Marburg vaccine is based on its properties to induce immune responses as readily as rAd5, but with little to no pre-existing immunity in human populations. The encoded WT GP antigens were chosen based on preclinical data and may provide protective immunity against Marburgvirus species and on their demonstrated safety in humans when expressed by a DNA plasmid.

1.3. Preclinical Studies Supporting Safety of cAd3 Constructs

The vaccine vector cAd3 has undergone several preclinical evaluations for other vaccine viral antigens. First, the vaccine vector, cAd3, was evaluated by others in an investigational HCV vaccine study; in support of clinical testing, nonclinical evaluations were performed for the vaccine, AdCh3-HCV (BB-IND 14818, Okairos, Inc.). In addition, a nonclinical toxicology study with VRC cAd3-HIV Vaccine (VRC-HIVADC064-00-VP) was performed by VRC/NIAID to support a clinical study. The toxicology studies demonstrated expected local inflammatory reactions, which were transient and failed to demonstrate unusual toxicities.

The March 2014 Ebola outbreak in West Africa [28] prompted the VRC/NIAID to accelerate initiation of the first chimp adenovirus vector clinical study – evaluation of VRC-EBOADC069-00-VP – a mix of two vectors: one expressing the WT GP Zaire and one expressing the WT GP Sudan. In April 2014, the VRC/NIAID proposed to the FDA that the prior nonclinical and clinical studies (AdCH3-HCV, cAd3-HIV) supported evaluation of cAd3-EBO through a staged, dose escalation Phase I study design without the conduct of a GLP toxicity study. The FDA concurred with the VRC proposal to proceed immediately with evaluation of the cAd3-EBO vaccine in a Phase I clinical trial. The VRC/NIAID with its collaborating researchers then sought and received approval to evaluate the cAd3 EBO GP Zaire vaccine alone as a vaccine under the same IND. This was designated VRC-EBOADC076-00-VP (cAd3-EBOZ).

Details of additional prior relevant nonclinical and clinical studies are summarized in the Investigator’s Brochure.

1.4. Nonclinical Protection Studies

Several non-GLP studies were performed in cynomolgus macaques to select filovirus constructs for further development and to provide animal proof- of-concept data before Phase I clinical studies. Research-grade materials, made with the same constructs as clinical material, for 1) Ebola - cAd3 EBO Z (containing GP from Ebolavirus Zaire), 2) Ebola - cAd3 EBO S (containing GP from Ebolavirus Sudan), 3) Ebola - cAd3-EBO (composed of a 1:1 ratio of cAd3 EBO Z and cAd3 EBO S), 4) Marburg – rAd5 Marburg GP, 5) Marburg GP DNA, and 6) cAd3 Marburg GP were used in the viral challenge studies summarized in Table 3 [22, 29]. In totality, these studies support Phase I clinical testing of the cAd3-Marburg vaccine; the protection studies in cynomolgus macaques are ordered in relevance to RV507.

Table 3: Preclinical Proof-of-Concept Studies in Cynomolgus Macaques

| Study Purpose | Study Outcome |
|---|--|
| Demonstrate protection against lethal challenge with Ebolavirus Zaire in cynomolgus macaques after single IM dose of cAd3 EBO Z | 100% protection after a single IM dose of cAd3 EBO Z at 10^{10} and 10^{11} vp |

| | |
|--|--|
| Demonstrate protection against lethal challenge with Ebolavirus Zaire after single IM dose of cAd3-EBO | 100% protection after a single IM dose of cAd3-EBO at 2×10^{10} vp 50% protection after cAd3-EBO at 2×10^9 vp |
| Demonstrate protection against lethal challenge with Ebolavirus Sudan after single IM dose of cAd3-EBO | 100% protection against Ebolavirus Sudan after a single IM dose of cAd3-EBO at 2×10^{10} vp |
| Demonstrate protection against lethal challenge of Marburg Angola after either a Marburg GP DNA vaccine, a single IM dose of Marburg GP rAd5-vector vaccine, or both | 100% protection from death when vaccinated with 4 IM 4mg dose of Marburg GP plasmid, or one IM dose of Marburg GP rAd5 at 10^{11} vp, or 3 IM 4mg dose of Marburg GP plasmid followed by one IM dose of Marburg GP rAd5 at 10^{11} vp |
| Demonstrate generation of humoral and cellular immune responses after single IM dose of cAd3-EBO at 2×10^9 or 2×10^{10} vp. | Single IM dose of cAd3-EBO at 2×10^9 vp or 2×10^{10} vp elicited antibody and antigen-specific CD4+ and CD8+ T cell responses. The lower cellular immune responses correlated with the lower level of protection (50%) observed after the 2×10^9 vp dose. |
| Demonstrate durability of the immune responses after single IM dose of cAd3 EBO Z at 10^{11} vp or cAd3-EBO at 2×10^{10} vp administered 10 months before the lethal challenge with Ebolavirus Zaire. | Protective immune responses measured during the acute phase of infection declined over time. When challenged 10 months after vaccination, 2/4 macaques were protected after a single IM dose of cAd3 EBO Z at 10^{11} vp while 0/4 were protected after a single IM dose of cAd3-EBO at 2×10^{10} vp. |
| Demonstrate protection against lethal challenge with Marburg Angola virus in cynomolgus macaques after single IM dose of cAd3-MARV and demonstrate durability of immune responses 12 months after vaccination. | 100% of animals challenged at 6 months and 75% challenged at 12 months survived |
| Demonstrate protection against lethal challenge of Marburg Angola after a single IM dose of cAd3-MARV | 100% protection after a single IM dose of cAd3-MARV GP at 1×10^{10} vp when challenged at 5 weeks post-immunization |

1.4.1. Protection against lethal MARV Challenge and Durability of Immune Responses after Single IM Injection with cAd3-MARV

Rapid onset of protection from a single administration of cAd3-MARV was demonstrated in a 5-week immunization/challenge experiment. At four weeks post-immunization, all NHPs that received at 1×10^{10} vp of the vaccine had ELISA titers to the Marburg GP with a mean titer of about 3×10^{10} . The macaques were challenged at 5 weeks post-immunization, and all vaccinated animals survived whereas the unvaccinated NHP did not. A second study evaluated the durability of the protective activity following a single administration of the vaccine. Macaques were immunized IM, and immune responses were evaluated at 4 weeks post-immunization. All animals had plasma anti-GP titers comparable to the first experiment (Figure 1). Groups of 4 animals were challenged with Marburg Angola at 6 months and 12 months post-immunization.

Unvaccinated controls did not survive the challenge. In contrast, all animals challenged at 6 months and 75% challenged at 12 months survived (Figure 2). These data demonstrated the immediate and durable protective activity of the vaccine in NHP.

Figure 1 Vaccine-induced antibody responses and protection against infectious challenge with Marburg Angola in macaques

[figure not shown]

Figure 1: Animals (n=4) were vaccinated by the IM route with at 1 x10¹⁰ vp of ChAd3-MARV GP. Antibody responses were assessed by MARV GP ELISA at 4 weeks post vaccination and animals were challenged with 1000 PFU Marburg Angola 1 week later.

Figure 2 Durability of vaccine-induced antibody responses and protection against infectious challenge with Marburg Angola in macaques

[figure not shown]

Figure 2: Animals (n=4/group) were vaccinated by the IM route with 1×10^{10} particles of ChAd3-MARV GP. Antibody responses were assessed at the indicated time points and animals were challenged with 1000 PFU Marburg Angola 6 or 12 months post-vaccination.

1.4.2. Protection against Marburg Angola After a Marburg GP DNA Vaccine, an IM Dose of Marburg GP rAd5-vectored Vaccine, or Both

Each monkey in the DNA vaccine group (n=4) was injected intramuscularly with 4 mg MARV GP DNA vaccine at 0, 4, 8 and 23 weeks by Biojector® 2000 needle-free injection device. Monkeys in the MARV rAd5 only group were injected IM by needle and syringe with 10^{11} vp. Three animals received MARV GP DNA weeks 0, 4, and 8 as above then boosted 12 weeks after the third DNA injection at 20 weeks with rAd5 MARV GP. There was 100% protection from death in animals vaccinated with all three regimens [22].

1.5. Dose Justification for cAd3-MARV

Quantification of the vaccine is based on cAd3 PU, and the doses chosen for phase I testing are based on those 1) shown to be protective in the accepted challenge model and 2) demonstrated to be safe in animal toxicity studies. Doses between 10^{10} and 10^{11} PU of cAd3 were safe and demonstrated partial to complete protection in NHP challenge studies. The doses of cAd3 vector expressing a variety of viral inserts have also been demonstrated to be safe in humans. Please refer to the IB for additional details.

2.0 STUDY OBJECTIVES

2.1. Primary Objectives

- To evaluate the safety and tolerability of VRC-MARADC087-00-VP when administered IM at a dose of 1×10^{10} particle units (PU) to healthy adults;
- To evaluate the safety and tolerability of VRC-MARADC087-00-VP when administered IM at a dose of 1×10^{11} PU to healthy adults.

2.2. Secondary Objectives

- To evaluate the antibody responses to the GP insert and cAd3 vector in VRC-MARADC087-00-VP at 4 weeks after vaccination as assessed by GP ELISA and vector-specific neutralization assays, respectively.
- To evaluate the Marburg GP-specific T cell responses in VRC-MARADC087-00-VP at 4 weeks after vaccination as assessed by ICS.

2.3. Exploratory Objectives

- To evaluate the immunogenicity of VRC-MARADC087-00-VP by various assay methods at some or all of the research sample collection timepoints indicated in the SOE; genetic factors associated with immune response may also be evaluated.
- To evaluate vaccine-induced mRNA expression profiles through Study Week 1.
- To evaluate the time course and durability of cAd3 neutralizing antibody titers, mediators of inflammation following vaccination and time course and durability of immune response by a variety of exploratory assays using samples collected throughout the study.
- To isolate MAbs to determine epitope specificity and their functional capacity.
- To evaluate plasmablasts to follow lineage development of anti-GP antibodies.

3.0 ENDPOINTS

3.1. Primary Endpoints: Safety

Assessment of product safety will include clinical observation and monitoring of clinical chemistry and hematology parameters. Safety will be closely monitored after injection and evaluated through 48 weeks after the study injection. The following parameters will be assessed for all study groups:

- Occurrence of solicited local reactogenicity signs and symptoms for 7 days following the vaccination
- Occurrence of solicited systemic reactogenicity signs and symptoms for 7 days following the vaccination
- Change from baseline for safety laboratory measures
- Occurrence of adverse events of all severities through 28 days after the study injection
- Occurrence of serious adverse events and new chronic medical conditions through the last study visit

3.2. Secondary Endpoints: Immunogenicity

Antibody titers, response rates and magnitudes will be the immunogenicity endpoints for the following assays where relevant: ELISA and antigen-specific and vector-specific neutralization assays and ICS assays for T cell responses. The principal time point for assessing antibody and T cell responses is Week 4 after vaccination.

3.3. Exploratory Endpoints

ELISpot assays to assess T and B cell responses at study timepoints shown in the SOE (Appendix 1), as well as evaluation of genetic factors associated with immune responses and time courses of immune responses may be completed as exploratory evaluations. MAbs may be isolated from cryopreserved peripheral blood mononuclear cells (PBMC) and evaluated to determine among other characteristics, epitope specificity, and functional capacity. Vaccine-induced mRNA expression profiles through 1 week after vaccination may also be performed as an exploratory evaluation. Plasmablasts will be isolated from whole blood at day 7 to evaluate immediate development of antibodies to Marburg GP.

4.0 STUDY DESIGN AND METHODS

This is a Phase I open-label, dose escalation clinical trial to evaluate the safety, tolerability and immunogenicity of cAd3-vectored vaccines for Marburg WT GP in healthy adults. The study will be conducted at the WRAIR CTC in Silver Spring, Maryland, USA.

Twenty participants will be enrolled in each of the two dosage groups for cAd3-Marburg. The study will begin with enrollment of 3 participants into Group 1. After at least 7 days of follow-up for the first 3 vaccinated participants, an interim safety review will occur before enrollment of additional participants into the group. If no safety issues are identified, an additional 17 participants will be enrolled to complete Group 1. When there is a minimum of seven days of follow-up safety data from the last enrolled participant in Group 1, an interim safety review will occur. Once no safety issues are identified, enrollment of participants into the next dose level will begin with the enrollment of 3 participants. After at least 7 days of follow-up for the first 3 vaccinated participants in Group 2, an interim safety review will occur before the enrollment of additional participants into Group 2. If no safety issues are identified, an additional 17 participants will be enrolled to complete Group 2. For the first 3 participants in each group, only one participant per day will be enrolled.

Study agent administration will be on Day 0. The study includes daily review of any new safety data by a study clinician and weekly review of safety data by the Protocol Safety Review Team (PSRT). The staged enrollment plan and plan for interim safety reviews (Section 7.3) applies to both Group 1 and Group 2. The interim safety reviews will be conducted by the PSRT.

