Screening evaluations for specific eligibility criteria (see Sections 4.1.1 and 4.1.2) must be completed within the screening visit window specified (Appendix 1) prior to enrollment, but may be repeated, if the initial laboratory result is not deemed medically significant, within the screening visit window in order to confirm eligibility. Samples for storage may also be collected within the screening visit window. Counseling on the potential risks of becoming pregnant during study participation will be provided. Pre-HIV test counseling and post-HIV test counseling will be provided during the screening process.

Study volunteers may be scheduled for a second Screening Visit to evaluate laboratory and test results if an abnormality or illness had been identified at the first screening. This approach will allow study staff to evaluate the recovery from any illness identified at the first screening as well as to repeat screening laboratory tests that were abnormal at the first screen due to transient illness.

Eligible and willing volunteers will be scheduled for an appointment for enrollment and the initial vaccination visit within 56 days of having satisfied eligibility requirements.

5.1.3. Day 0 Through Week 48

Day 0 is defined as the day of protocol enrollment and the study injection. Study eligibility criteria are reviewed on Day 0 as part of the enrollment process. If clinical assessment on Day 0 suggests significant changes may have occurred since the screening visit, then the physical examination, hematology tests, blood chemistries, and urinalysis done at screening must be repeated, as appropriate, before the participant receives the experimental vaccine. Pregnancy test results for women of childbearing potential must be obtained prior to the study injection. Day 0 evaluations immediately prior to the first injection are the baseline for subsequent safety assessments.

Refer to the table in Appendix 1 for details on the SOE and the window(s) permitted. After Day 0, deviations from the visit windows in completing study visits are discouraged and will be recorded as protocol deviations, but are permitted, at the discretion of the PI (or designee), in

consultation with the sponsor, in the interest of obtaining participant safety and immunogenicity evaluations following exposure to the investigational vaccine.

Study visit procedures and tests through Week 48 include the following as indicated in the SOE (Appendix 1):

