Participants will be given a “Diary Card”, a thermometer, and a ruler. The diary card will be used as a memory aid, on which the participant will record temperature, local and systemic symptoms and concomitant medications daily for 7 days after the injection. Participants will be trained to complete the paper diary card, how to use the thermometer, and how to measure injection site swelling and redness using the ruler. Completion of the diary card training will be noted in source documents. The written (paper) diary card will be transcribed into the study database and will be stored in the participant file for monitoring purposes.

The solicited signs and symptoms on the diary card (among others) will include: joint pain, unusually tired, muscles aches (other than at injection site), headache, chills, nausea, and pain at injection site. Participants will also record the day’s highest measured temperature and measurement of largest diameter for redness and swelling at the injection site. The completed diary cards are collected at the first visit following completion of the 7-day diary card (about 2 weeks after the injection).

Follow-up on participant well-being will be performed by telephone or clinic visit on the day following vaccination and by clinic visit on Day 3 following the injection to assess their clinical status. Participants may call or come to the clinic at any time-point for evaluation, if they experience unusual, moderate or severe signs and symptoms. Diary cards will be reviewed with the clinician at any visit from day of vaccination through the first study visit following completion of the diary card. If upon reviewing the clinician finds that general symptom or injection site symptom information (except swelling or redness measurements) is missing from the diary cards, the participant will be asked to provide the missing information to the best of their recollection.

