7.3. Protocol Safety Review Team

The PSRT will review all AEs (including reportable AEs) on a regular and expedited basis as needed. In addition, the PSRT will review aggregate safety data reports on a weekly basis until 4 weeks after all participants have completed the vaccination, then the safety reviews will occur monthly. The PSRT will review SAEs that potentially meet study pause criteria on an expedited basis and will decide if the study should be paused for participant safety purposes. This team includes the following: Principal Investigator or designee, Associate Investigators, Protocol Consultants, DoD Research Monitor, sponsor IND Medical Officer or designee, and other VRC Representatives. Additional participants could include study personnel and senior clinical research nursing staff. A quorum is established with the PI or designee, one AI or designee, and IND Medical Officer or their designee. If the DoD Research Monitor is not available for the PSRT call, they must provide input by email and then be immediately emailed the outcome of the PSRT discussion.

In addition to the regular and expedited meetings, the PSRT will conduct the following three interim safety data reviews to assess whether or not the safety data meet criteria for moving on to the next stage of the study.

Review for Continuation of 1×10^{10} PU Dose of VRC- MARADC087-00-VP: No more than 1 participant per day will be enrolled into the group for the first 3 participants. When the first 3 participants who have received the 1×10^{10} PU dose have completed post vaccination follow up through at least the “Study Day 7” visit, an interim safety data review will be conducted by the PSRT. Enrollment of the remaining 17 participants in the group may proceed if the PSRT assesses the data as safe to continue.

Review for Dose Escalation to 1×10^{11} PU Dose of VRC- MARADC087-00-VP: When the last participant who has received the 1×10^{10} PU dose has completed post vaccination follow up through at least the “Study Day 7” visit, an interim safety data review will be conducted by the

PSRT. If the safety data support proceeding to the 1×10^{11} dose, then enrollment of Group 2 will begin.

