Review for Continuation of 1×10^{11} PU Dose of VRC- MARADC087-00-VP: No more than 1 participant per day will be enrolled into the group for the first 3 participants. When the first 3 participants who have received the 1×10^{11} PU dose have completed post vaccination follow up through at least the “Study Day 7” visit, an interim safety data review will be conducted by the PSRT. Enrollment of the remaining 17 participants in the group may proceed if the PSRT assesses the data as safe to continue.

After each of these interim safety reviews, the IRB and VRC will be provided with documentation of the safety review and notification of the plan.

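### The dose-escalation review is tied to the last-enrolled Group 1 participant, so other participants' in-window Day 7 visits can still be outstanding by up to 3 days

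*Combined protocol and SAP*

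**What the plan says.** The escalation review is described in three places.

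- **Schema and Section 4.0.** The review is due "When there is a minimum of seven days of follow-up safety data from the last enrolled participant in Group 1". The marker is one person, identified by order of enrolment.
- **Section 7.3, escalation review.** The sentence opens "When the last participant who has received the" lower dose and goes on "has completed post vaccination follow up through at least the “Study Day 7” visit, an interim safety data review will be conducted by the" PSRT. It asks for a completed visit rather than elapsed days, but is still keyed to one participant.
- **Section 7.3, reviews after the first 3 in each group.** These open "When the first 3 participants who have received the" dose in question, and the plural verb requires all three to have completed the Day 7 visit.

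The timing provisions are elsewhere. Section 5.1.3 states: "Day 0 is defined as the day of protocol enrollment and the study injection". Appendix 1 gives visit 02A (Day 1) a window of +1 day, 02B (Day 3) +2 days and 02C (Day 7) +3 days. Section 4.0 limits enrolment to one per day for the first 3 in each group and sets no rate for the other 17. Under Section 5.2.1 participants are seen "by clinic visit on Day 3 following the injection to assess their clinical status", and "Diary cards will be reviewed with the clinician at any visit from day of vaccination" up to the first visit after the card is finished.

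**The concern.** The protocol asks for complete Day 7 visits before it adds 17 people at a dose already given to 3. It does not clearly ask for the same before moving to a tenfold higher dose of a vaccine that, by Section 1.2, has no prior human experience.

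Because enrolment and injection share Day 0, seven days after the last injection means at least seven days after everyone's injection. Elapsed time is therefore not the problem. The problem is the visit window: a participant dosed shortly before the last one, or on the same day, may properly attend later than the last one does. For that person the latest scheduled contact is the Day 3 visit. The Day 7 history, targeted examination and diary review would not yet exist when the PSRT meets.

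This could matter because Section 7.4 pauses the study when two participants have the same related Grade 3 or 4 event, and Section 7.2 brings solicited reactions within the pause rules. An outstanding visit could hold the second such event.

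**Working it through.** The plan states no figure on this point, so there is none to reproduce. The check is calendar arithmetic.

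**Inputs from the protocol.** Visit 02C falls on Day 7 to Day 10, and visit 02B on Day 3 to Day 5 (Appendix 1). Day 0 is the day of injection (5.1.3). Seventeen participants follow the first 3, with no rate limit (4.0).

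**Lag.** Let L be the day the last Group 1 participant is dosed. The earliest review is L+7, when that person attends on Day 7. Someone dosed on L−k has an in-window visit as late as L−k+10. The maximum lag is (L−k+10) − (L+7) = 3−k days, or zero if that is negative. If the last participant attends on Day 8, 9 or 10, the largest lag falls to 2, 1 or 0 days.

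The Day 3 visit cannot be outstanding in window: its latest date is L−k+5, which is before L+7 for every k ≥ 0.

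**Chance that a visit is outstanding.** Assume the visit days V (this participant) and V_last (last participant) are independent and uniform on Days 7, 8, 9 and 10. A visit is outstanding when V − k > V_last. Counting the 16 equally likely pairs gives:

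| k | Latest in-window visit | Lag at L+7 (days) | P(outstanding) | P given V_last = 7 |
|---|---|---|---|---|
| 0 | L+10 | 3 | 6/16 | 3/4 |
| 1 | L+9 | 2 | 3/16 | 1/2 |
| 2 | L+8 | 1 | 1/16 | 1/4 |
| 3 | L+7 | 0 | 0 | 0 |

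**Number of visits.** Assume the 17 are enrolled on consecutive days at a constant rate. At 1, 2 or 3 per day the final day holds 1, 1 or 2 people (17 = 17×1; 8×2+1; 5×3+2). The numbers of other participants at k = 0, 1, 2 follow.

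| Assumed rate | Others at k = 0, 1, 2 | Maximum outstanding | Mean, uniform visits | Mean if V_last = 7 |
|---|---|---|---|---|
| 1/day | 0, 1, 1 | 2 | 3/16 + 1/16 = 0.25 | 1/2 + 1/4 = 0.75 |
| 2/day | 0, 2, 2 | 4 | 6/16 + 2/16 = 0.50 | 1 + 1/2 = 1.5 |
| 3/day | 1, 3, 3 | 7 | 6/16 + 9/16 + 3/16 = 1.125 | 3/4 + 3/2 + 3/4 = 3.0 |

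**What is missing for each outstanding visit.** The diary covers 8 days (Day 0 to Day 7). After a Day 3 visit held on Day 3, the 4 entries for Days 4–7 have not been reviewed at a scheduled visit. If that visit was on Day 5, 2 entries remain (Days 6–7). No safety laboratory result is affected: the 78 mL drawn at 02C is fully accounted for by serum 12 + PBMC 60 + RNA 6.

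**The case against.** The strongest reply is that Section 7.3 is the operative text. Section 4.0 points to it for the interim review plan, and the Schema and 4.0 describe all three reviews loosely in elapsed time. On that view the last participant in 7.3 means the last to complete, and there is no gap. The reading is possible, but it is not the literal one, and the reference in 4.0 and the Schema to the last enrolled participant cannot be read that way. An escalation rule should not depend on which section is consulted.

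The other points are sound, and they limit the size of the problem:

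- The seven days are a minimum. The PSRT may wait, and Group 2 opens only if the data support it.
- New safety data are reviewed daily by a clinician and weekly by the PSRT. Participants may call or attend at any time, and the pause rules continue to apply.
- Section 11.3.1 says that systemic reactions typically occur on the day of vaccination or the next day, earlier than the entries at issue.
- The gap closes before the next review. If Group 2 dosing began on L+7 at one per day, the third person would be dosed on L+9 and the next review could not occur before L+16. All in-window Group 1 Day 7 visits close by L+10.
- The full 3-day lag needs same-day dosing, one participant seen on Day 7, another on Day 10, and a review held at once.
- Completing the Day 7 visit does not guarantee a finished diary. Cards are collected at about 2 weeks, and a person seen on Day 7 may not have made that day's entry.

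These safeguards reduce the consequence. They do not make the stated minimum require the Day 7 visits.

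**Conclusion.** The concern holds. As worded in the Schema and 4.0, and on the literal reading of 7.3, the escalation review can take place while in-window Day 7 visits are outstanding: by at most 3, 2 or 1 days for people dosed 0, 1 or 2 days before the last participant, and not at all for those dosed earlier. That result needs only the visit window and the absence of an enrolment limit. The counts of outstanding visits also rest on the assumed enrolment rates, and the means on the assumed uniform visit timing.

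The practical effect is small and touches no endpoint, analysis or sample size. The change is still worth making, because it is cheap and brings the escalation review to the standard that 7.3 already applies to the first 3 participants in each group.

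**What to change.** Replace the escalation trigger in the Schema, 4.0 and 7.3 with one rule: *the review is held when all Group 1 participants who received the injection have completed the Study Day 7 visit, or have a documented missed visit or withdrawal with all available safety data given to the PSRT.* The second clause keeps one absent participant from blocking escalation. It also covers late visits, which 5.1.3 permits as deviations and to which the 3-day bound does not apply.

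Leave the two reviews after the first 3 participants in 7.3 as they are. PSRT discretion is unchanged.

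The cost is one sentence in three places. With visits in window, the earliest review moves from L+7 to L+10 at the latest, a delay of 0 to 3 days. No procedure, visit or sample size changes.
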